## PROTOCOL SYNOPSIS

**Title:** A Multicenter, Randomized, Double-Blind, Placebo-Controlled Phase 3 Trial to Evaluate Efficacy and Safety of Lenabasum in Dermatomyositis

### Objectives and Endpoints:

Primary Objective	Primary Efficacy Endpoint
To evaluate the efficacy of lenabasum compared to placebo in subjects with dermatomyositis (DM)	
Total Improvement Score (TIS) by the 2016 American College of Rheumatology (ACR)/European League Against Rheumatism (EULAR) Myositis Response Criteria at Week 28
 
The TIS is comprised of 6 core set measures and absolute value and change from baseline in each core set measure will be presented to support the composite TIS:
 

1. Physician global activity (MDGA)

2. Patient global activity (PtGA)

3. Manual Muscle Testing (MMT)

4. Health Assessment Questionnaire (HAQ)

5. Muscle enzymes

6. Extramuscular global activity (EMGA)

 
A MMT that assesses strength in 8 muscle groups (MMT-8) will be used in this study.

Secondary Efficacy Endpoints	
	
The following endpoints will be compared in lenabasum 20 mg BID and placebo cohorts and lenabasum 5 mg BID and placebo cohorts at Week 28, unless otherwise specified. All outcomes involving continuous variables will be assessed as absolute values and, if relevant, change from Baseline. All categorical variables will be assessed as number and proportion of subjects in each category:
 

1. Subjects who achieve Definition of Improvement (DOI), defined as <math>\geq 3</math> of 6 core set measures improved by <math>\geq 20\%</math> (relative to Baseline) with no more than 2 core set measures worsening by <math>\geq 25\%</math> (MMT-8 may not decrease by <math>\geq 25\%</math> from baseline)

2. Subjects who improve by at least one category on the Investigator Global Assessment (IGA) scale of skin activity

3. Subjects who achieve TIS <math>\geq 40</math> (at least moderate improvement)

	

4. TIS in subjects receiving any immunosuppressant medication for > 1 year at Baseline

5. TIS at Visit 10 (Week 52)

6. Cutaneous Dermatomyositis Disease Area and Severity Index (CDASI) activity score

7. TIS (lenabasum 5 mg compared to placebo cohorts only)

	Tertiary Efficacy Endpoints
	
These endpoints will be assessed at all visits at which they are measured, if not already included as the primary or secondary efficacy endpoints. Additional tertiary efficacy endpoints may be included in the Statistical Analysis Plan (SAP).

	
Change from Baseline compared to placebo in physician or laboratory assessments:
 

1. Forced vital capacity (FVC) absolute change in mL and percent predicted

2. CDASI damage score

3. MDGA (Likert Scale)

4. Corticosteroid dose

 
Change from Baseline compared to placebo in patient reported outcomes:
 

1. Functional Assessment of Chronic Illness Therapy (FACIT)-Fatigue Score

2. 5-D Itch Score

3. National Institutes of Health Patient-Reported Outcomes Measurement Information System (PROMIS)-29 Short Form domain scores

4. Patient Visual Analog Scale (VAS) scores of Pain

5. Skindex-29+3

6. European Quality of Life 5-domain (EQ-5D) questionnaire score

7. SF-36 domain scores

 
Proportion of subjects:
 

1. Achieving a CDASI activity score of <math>\leq 14</math>

2. Achieving clear or almost clear skin on the IGA scale of skin activity

3. Achieving a TIS of <math>\geq 20</math>, <math>\geq 40</math>, and <math>\geq 60</math>

	

4. Achieving a reduction in dose of any immunosuppressive medication (including corticosteroid) for > 28 days, among subjects receiving immunosuppressive medications at Baseline

5. Requiring an increase in dose of any immunosuppressive medication (including corticosteroids), or rescue immunosuppression for > 28 days

 
Subset analyses of outcomes above by Baseline characteristics:
 

1. TIS by: MMT-8 score and other core set measures as continuous variables

2. TIS and core set measures and secondary outcomes by: age (continuous variable); geographic region (US, ex-US); any non-corticosteroid immunosuppressive treatment (yes, no); dose of oral prednisone or equivalent

 
Minimal Important Difference (MID):
 

1. Determine MID in TIS, HAQ-DI and CDASI in DM

2. Subset analysis to determine proportion of subjects that achieve MID in TIS, HAQ-DI and CDASI

--	--

Secondary Objective	Safety Endpoints
To evaluate the safety and tolerability of lenabasum in subjects with DM	

1. Adverse events (AEs)

2. Changes in vital signs, physical examinations, blood and urine laboratory safety tests, and ECGs associated with lenabasum treatment

3. Number of subjects who permanently discontinue study product due to AEs probably- or definitely-related to treatment

Tertiary Objectives	Tertiary Endpoints and Evaluations
[REDACTED]	[REDACTED]
Additional Objectives	Additional Endpoints
To evaluate the long-term efficacy and safety of lenabasum in completed subjects who continue to receive treatment in an optional open-label extension (OLE)	
In an open-label extension (OLE) phase (Part B):
 

1. Evaluate long-term signals of efficacy

2. Evaluate long-term safety

**Study Design:** This is a Phase 3, multicenter, interventional, double-blind, randomized, placebo-controlled study designed to assess the efficacy and safety of lenabasum in subjects with DM.

The study consists of 2 parts:

- Part A: Double-Blind, Placebo Controlled Phase
- Part B: Open Label Extension Phase (Optional)

The overall design for this study is summarized in [Figure 1](#) of the protocol.

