## 4. STUDY POPULATION

### 4.1. Inclusion Criteria

Subjects must meet ALL of the following criteria to be eligible for the study:

1. Able to understand and voluntarily sign the informed consent
2. Male or female  $\geq 18$  years of age at the time of signing the informed consent
3. Fulfill one of the following criteria for DM:
  - a. Bohan and Peter's criteria for probable or definite DM ([Bohan and Peter, 1975a](#); [Bohan and Peter 1975b](#))
  - b. ACR/EULAR criteria ([Lundberg et al, 2017](#))
4. Subject has active DM as determined by the investigator
5. Disease activity/severity fulfils one of the following three criteria:
  - i. MDGA  $\geq 3$  cm (0-10 cm scale) and MMT-8 score  $\leq 142$  (out of 150 total possible)
  - ii. Sum of MDGA, PtGA and EMGA VAS scores is  $\geq 10$  cm (all scales individually on 0-10 cm scale)
  - iii. MDGA  $\geq 3$  cm and CDASI activity score of  $>14$
6. Stable doses of immunosuppressive medications for DM as defined by:
  - a. Unchanged dose of oral corticosteroids  $\leq 20$  mg per day prednisone or equivalent for  $\geq 4$  weeks before Visit 1
  - b. Unchanged dose of immunosuppressive medications other than oral corticosteroids for  $\geq 8$  weeks before Screening
7. Willing to not start or stop any immunosuppressive medications for DM from Screening through end of study, unless a change is part of the protocol or considered in the subject's best medical interest by the site investigator or another physician who has primary responsibility for treating the subject's DM.
8. Willing to not use any cannabinoids, including recreational marijuana, medical marijuana and other prescription cannabinoids from Screening through end of study.
9. Able to adhere to the study visit schedule and other protocol requirements and follow study restrictions.
10. Women of childbearing potential (WOCBP) must not be pregnant or breastfeeding and they or their male sexual partner must be using at least one acceptable method of contraception (see [Appendix 1](#)) for at least 4 weeks before Visit 1 and be willing to continue its use for at least 4 weeks after discontinuation of study product.

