### **8.1.5. Investigator Global Assessment (IGA) scale of skin activity**

The IGA is a 5-point scale to evaluate overall skin disease by the investigator. Skin will be assessed as clear, almost clear, mild, moderate, or severe based on the overall description of each category as provided in [Appendix 2](#).

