### **8.1.22. Skin Biopsies**

Skin biopsies (at Baseline, Visit 4, and at and at the end of treatment [Visit 10 or Early Termination]) will be collected in consenting subjects at selected sites. Five 4mm skin biopsies will be collected (other than site 1001) 2 each at Visit 1 and Visit 4 respectively for histology and transcriptome and 1 at Visit 10 for transcriptome. The biopsies will preferentially be taken from an area of involved skin that is active or worsening, rather than improving, in the opinion of the site investigator. No biopsies will be taken from the face, neck, hands or feet. Biopsies should be taken from the same location at each biopsy visit, provided that this area is active or worsening at that timepoint. If a subject has no active skin involvement in an area that can be biopsied at Visit 1, then no biopsies should be taken at Visit 1 or any subsequent visit (because there will be no Baseline biopsy for comparison). If biopsies are obtained at Visit 1, then subsequent biopsies should be obtained within 1-2 cm of the first biopsy sites, without regard to disease activity at that site at that time.

Histology will be evaluated by a blinded pathologist post-treatment and compared to Baseline. Flow cytometry may be conducted to analyze cell subsets in the skin and transcriptome analysis may be performed to assess RNA levels. Skin biopsy results may be reported separately from the main CSR.

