### 9.3. Populations for Analyses

There are 4 analysis populations defined in this study:

**The modified intent to treat (mITT) population** will consist of all randomized subjects who have received at least one dose of study product. Analysis of the modified ITT population will be used as the primary efficacy analyses and will analyze subjects under the treatment to which they were randomized, regardless of compliance with assigned treatment.

**The per protocol (PP) population** will consist of subjects who complete the study without major protocol violations deemed likely to affect the efficacy outcomes of interest (these deviations will be classified during a blinded deviation review meeting before unblinding the study). Analysis on the PP population will be used as secondary efficacy analyses, analyzing subjects under the treatment actually received.

**The safety population (SAF)** will consist of all subjects who received any study product. Analysis performed on the safety population will be according to the treatment actually received.

**The pharmacokinetic (PK) population** will consist of all subjects from the SAF whose pharmacokinetic data are adequate for the calculation of primary PK parameters. Inclusion in the PK population of subjects with missing data or protocol violations or inadequate dosing will be considered on a case-by-case basis. The PK population will be the analysis set used for all pharmacokinetic analyses.

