## **9.4. Statistical Analyses**

### **9.4.1. General Approach**

All data will be provided in data listings sorted by treatment group, subject number, and visit. Summary data will be presented in tabular format by treatment group. Categorical data will be summarized by the number and percentage of subjects in each category. Continuous data will be summarized by descriptive statistics including the sample size (n), mean, standard deviation, median, minimum and maximum. All percentages will be rounded to one decimal place. Differences between treatment groups will be calculated as lenabasum placebo and change from Baseline will be calculated as visit Baseline. The Baseline measure will be defined as the last non-missing measure before initiation of study product.

Data will be presented by randomized treatment group for efficacy data and by actual treatment group for safety data.

P-values and 2-sided 95% confidence intervals will be presented for all efficacy endpoints.

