#### **9.4.1.2. Adjustments for Multiplicity**

The overall type I error rate will be controlled for primary and secondary outcomes with a hierarchical ordering of assessments. The order of the tests for treatment effect will be as follows:

- Primary efficacy outcome: Mean TIS, lenabasum 20 mg BID versus placebo, at Week 28.
- Secondary efficacy outcomes (Change from Baseline at Week 28):

The following endpoints will be compared in lenabasum 20 mg BID compared to placebo cohorts and lenabasum 5 mg BID compared to placebo cohorts at Week 28. All outcomes involving continuous variables will be assessed as absolute values and, if relevant, change from Baseline. All categorical variables will be assessed as number and proportion of subjects in each category. The list will be done in order below for comparisons between lenabasum 20 mg BID and placebo cohorts:

- Subjects who achieve DOI
- Subjects who improve by at least one category on the IGA scale of skin activity
- Subjects who achieve TIS  $\geq 40$  (at least moderate improvement)
- TIS in subjects receiving any immunosuppressant medication for  $> 1$  year at Baseline
- TIS at Week 52
- CDASI activity score

The list will continue in order below for comparisons between lenabasum 5 mg BID and placebo cohorts:

- TIS
- Subjects who achieve DOI Subjects who improve by at least one category on the IGA scale of skin activity
- Subjects who achieve TIS  $\geq 40$  (at least moderate improvement)
- TIS in subjects receiving any immunosuppressant medication for  $> 1$  year at Baseline
- TIS at Week 52
- CDASI activity score

Note that, in Part A, statistical significance for each endpoint must first be achieved in order to continue in the assessment of the next endpoint, following the testing sequence above.

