#### **9.4.3. Analysis of the Secondary Efficacy Endpoint(s)**

[figure not shown]
Continuous secondary and tertiary outcome variables will be analyzed similarly to the primary MMRM model, using change from Baseline as the dependent variable, with the Baseline of each endpoint also included in the model. Other outcomes based on the proportion of subjects achieving defined criteria will be analyzed using a Fisher's exact or Cochran-Mantel-Haenzel test.

Secondary efficacy endpoints in this study include:

1. Subjects who achieve DOI
2. Subjects who improve by at least one category on the IGA scale of skin activity
3. Subjects who achieve TIS  $\geq 40$  (at least moderate improvement)
4. TIS in subjects receiving any immunosuppressant medication for  $> 1$  year at Baseline
5. TIS at Visit 10 (Week 52)
6. CDASI activity score

7. TIS (lenabasum 5 mg compared to placebo cohort only)

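### Low-weight, cheap improvement: the gatekept IGA responder endpoint sets no baseline-IGA condition, so subjects with clear skin at entry cannot respond and the risk difference is multiplied by (1−f)

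*Protocol*

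**What the plan says.** The synopsis (Objectives and Endpoints) lists as a secondary endpoint "Subjects who improve by at least one category on the Investigator Global Assessment (IGA) scale of skin activity". Section 2, Section 9.4.1.2 and Section 9.4.3 repeat it, each time without a baseline condition.

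- **Scale.** Section 8.1.5: "Skin will be assessed as clear, almost clear, mild, moderate, or severe". *Clear* is the best of five categories.
- **Entry.** Section 4.1, criterion 5: "Disease activity/severity fulfils one of the following three criteria". Route i uses MDGA and MMT-8, route ii a sum of three global scales. Only route iii asks for skin activity (CDASI activity above 14).
- **Population.** Section 9.3: the mITT set "will consist of all randomized subjects who have received at least one dose of study product".
- **Test.** Section 9.4.3: "Other outcomes based on the proportion of subjects achieving defined criteria will be analyzed using" Fisher's exact or a CMH test. No CMH strata are named.
- **Sequence.** Section 9.4.1.2: "statistical significance for each endpoint must first be achieved in order to continue in the assessment of the next endpoint". For 20 mg the order is TIS, DOI, IGA, then four more tests, then seven tests for 5 mg.
- **Baseline.** Section 9.4.1: "The Baseline measure will be defined as the last non-missing measure before initiation of study product".
- **Window for change.** Section 2 closes by leaving endpoints to be finalized in the SAP before unblinding.

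**The concern.** A subject rated *clear* at baseline has no better category to move to and counts as a non-responder whatever the treatment. A subject rated *almost clear* can still respond. Subjects who cannot respond dilute both arms' response rates and carry no information about the treatment.

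The protocol foresees something close to this. Section 8.1.22 provides for the case "If a subject has no active skin involvement in an area that can be biopsied at Visit 1". That is weaker evidence than it looks: face, neck, hands and feet are not biopsied, so such a subject need not be IGA *clear*, and no frequency is given.

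Elsewhere the protocol does set baseline conditions. An enzyme improvement counts towards DOI only if the enzyme was above normal at Baseline (Section 8.1.3), and the tertiary dose-reduction endpoint is limited to subjects on immunosuppressants at Baseline. The IGA endpoint has no counterpart.

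At stake is some power at a gate with eleven tests behind it (four for 20 mg, seven for 5 mg), and a responder rate whose denominator includes subjects who could not respond.

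**Working it through.** **The plan's own figure.** There is no power calculation for IGA. The one for TIS reproduces: 48 per arm, difference 15, SD 20, two-sided 0.05 gives 15 / (20 × √(2/48)) = 3.674 and power Φ(3.674 − 1.960) = 0.957 (0.953 with the t distribution), against 95% stated.

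**Dilution.** Let pT and pC be the response rates among subjects not clear at baseline, and f the share clear in each arm (equal in expectation; Section 5.3 does not stratify on skin activity). The all-mITT rates are (1−f)pT and (1−f)pC, so the difference is (1−f)(pT − pC). The rate ratio is unchanged.

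**Power.** From the protocol: 60 / 30 / 60 dosed (Section 9.2) and two-sided 0.05. Assumed: pC = 25%, pT = 50%, and f. All figures are by full enumeration. *Restricted* means only subjects not clear: for Fisher, 60(1−f) per arm (57, 54, 48, 42); for CMH (one stratum, no continuity correction), a binomial number clear in each arm. At f = 0, power is 76.0% (Fisher) and 81.4% (CMH).

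| f | Difference, all mITT (points) | Fisher: all → restricted (%) | Gain | CMH: all → restricted (%) | Gain |
|---|---|---|---|---|---|
| 5% | 23.8 | 72.1 → 73.2 | 1.2 | 78.0 → 79.7 | 1.7 |
| 10% | 22.5 | 68.1 → 71.9 | 3.8 | 74.4 → 77.5 | 3.1 |
| 20% | 20.0 | 60.0 → 64.3 | 4.3 | 67.1 → 72.4 | 5.3 |
| 30% | 17.5 | 51.0 → 59.9 | 8.9 | 58.8 → 66.4 | 7.7 |

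Gains are taken before rounding. Most of the loss cannot be recovered: with CMH at f = 20%, power falls 14.3 points (81.4 to 67.1) and restriction returns 5.3.

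**As sample size.** The subjects needed without restriction, relative to with it, are (1 − (1−f)p̄)/(1 − p̄). With p̄ = 0.375 this is 1.03, 1.06, 1.12 and 1.18 at f = 5, 10, 20 and 30%.

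**5 mg versus placebo (30 vs 60).** With CMH the gains are 1.4, 2.6, 4.0 and 4.9 points at the same f. With Fisher at fixed counts, power falls from 59.7% to 58.3% at f = 2% (29 vs 59) and from 57.5% to 56.3% at f = 5% (28 vs 57). The sign reflects the discreteness of the exact test: 30 × 0.95 = 28.5, and taking 29 instead of 28 gives 60.5%.

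**Stratified CMH.** A stratum with m responders among N subjects contributes (responders on active) − n₁m/N to the numerator and n₁n₂m(N−m)/(N²(N−1)) to the variance. In the clear stratum m = 0, so both are zero. The statistic equals that of the restricted analysis exactly.

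**The case against.** **The SAP may settle it.** The denominator of a responder endpoint is often fixed there, and Section 2 leaves endpoints open until unblinding. The unseen SAP may already contain the condition. But the protocol does not leave the rule blank: it states responder rule and population wherever the endpoint appears. The sentence in Section 2 shows when a change can be made, not that it has been made.

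**All-mITT is a legitimate choice.** It fits the aim in Section 3.2.1 of enrolling patients with the full range of DM manifestations, and restriction narrows the claim. This stands, and is why the point is not an error.

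**A permitted test already removes the recoverable loss.** CMH stratified by clear versus not clear does so, as shown above. This stands too; it does not help if Fisher's test is used.

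**The size is unknown.** This also stands. Every subject has dermatomyositis, route iii requires skin activity, and *almost clear* subjects can improve, so f may be small.

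**Stronger readings a reader might infer.** One is that the comparison is biased or invalid; it is not, since subjects who cannot respond dilute both arms alike in expectation and the null rejection rate is kept. Another is that the wording puts the eleven later tests in jeopardy. The gate is reached only if TIS and DOI have succeeded, and only the recoverable points above are due to the wording. A third is that f is 20 to 30%; nothing in the protocol supports that, and the biopsy provision gives no share.

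**Conclusion.** The point holds at low weight. The endpoint has no baseline-IGA condition, subjects with clear skin are eligible, and the all-mITT risk difference is multiplied by (1−f); that is, it shrinks by the fraction f. This follows from the text and needs no assumption beyond an equal expected f in the two arms.

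The power consequence rests on assumed response rates (25% vs 50%) and an assumed f. At 60 per arm it is about 1 to 2 points at f = 5% and 3 to 4 at f = 10%. The 4 to 9 points at f = 20 to 30% are illustrative only. If few subjects are clear the gain is negligible, and for 5 mg with Fisher's test at f = 2 to 5% it can be slightly negative at fixed counts. The primary endpoint is untouched.

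**What to change.** Before unblinding, adopt one of two wordings.

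1. Make the gatekept IGA comparison in mITT subjects whose baseline IGA is worse than *clear*, and report the all-mITT result as supportive. IGA is scheduled at Screening and Visit 1 and baseline precedes the first dose, so the subset does not depend on treatment and the randomized comparison is preserved. Cost: a smaller denominator and a claim limited to subjects with some skin activity at baseline.
2. Keep all mITT subjects and name the CMH test, stratified by baseline IGA clear versus not clear. It gives the same test without narrowing the population. Cost: the plan commits to CMH rather than Fisher for this endpoint, and the reported all-subject risk difference stays diluted.

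Either is one line of text and needs no new data. Whichever is chosen, apply it to both dose comparisons and report the number clear at baseline by arm.

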### **Part A Double-Blind, Placebo Controlled Phase**

The initial plan is for approximately 150 dosed subjects to receive at least 1 dose of study product. The final number of subjects to be dosed will be decided after a blinded interim analysis. The timing and methods for the interim analyses will be outlined in the statistical analysis plan (SAP). It is expected that approximately 200 subjects will be screened to dose 150 subjects. Subjects will be randomized to receive lenabasum 20 mg, lenabasum 5 mg, or placebo twice-daily (BID) in a 2:1:2 ratio. It is hypothesized that subjects receiving lenabasum will have greater improvement in the TIS score (2016 ACR/EULAR Myositis Response Criteria) at Week 28 compared to subjects receiving placebo.

The total duration of participation for an individual subject is approximately 60 weeks and includes the following: a screening visit (up to 4 weeks before Visit 1), up to 52-week treatment period, and a Safety Follow-up Visit that will be conducted  $4 \pm 1$  weeks after the last visit. Subjects will be assessed for safety and efficacy parameters every 6 weeks (except for Visit 2, which will occur 4 weeks after Visit 1) for a total of up to 10 treatment visits. Study personnel will also contact subjects by telephone halfway between Visit 9 and Visit 10 (Week  $49 \pm 1$ ) to assess compliance, safety and overall status of DM, if applicable.

A subject's corticosteroid or other immunosuppressant treatments may be reduced if the investigator determines that clinical improvement in the subject's dermatomyositis has occurred and a reduction is warranted. It is recommended that a reduction in corticosteroid or immunosuppressant treatment should not occur before Visit 4 or after Visit 8. A preferred schedule for reduction is provided in [Section 5.5.1](#) of the protocol.

